2.2.2 Rationale for Clinical Investigation of GamaSTAN

GamaSTAN is manufactured from human plasma employing caprylate/chromatography steps in the purification scheme. This production process yields a final IgG product that is purer and more closely reflects the IgG subclass distribution found in plasma than earlier IgG products ^(12, 13). GamaSTAN is being developed for the same indications as those of GamaSTAN S/D including pre-exposure prophylaxis for persons travelling to areas with endemic HAV.

2.3 Known and Potential Risks and Benefits to Human Subjects

Because GamaSTAN is made from human plasma and is therefore a biological product, it may carry a risk of transmitting infectious agents (e.g., viruses and, theoretically, the Creutzfeldt-Jakob disease (CJD) agent). No cases of transmission of viral diseases or CJD have ever been identified for other products manufactured with the same caprylate/chromatography purification process. The risk that GamaSTAN can transmit an infectious agent has been reduced by screening plasma donors for prior exposure, testing donated plasma, and by the inclusion of steps in the manufacturing process with the demonstrated capacity to inactivate and/or remove pathogenic agents. Despite these measures, it may carry a risk of transmitting infectious agents. ⁽⁹⁾

There is clinical evidence of an association between the administration of all immunoglobulins and thromboembolic events such as myocardial infarction, stroke, pulmonary embolism and deep vein thrombosis. Therefore, caution should be exercised when prescribing and administering immunoglobulins. Thrombosis may occur even in the absence of known risk factors.

GamaSTAN should be given with caution to subjects with a history of prior systemic allergic reactions following the administration of human IG preparations ⁽¹⁴⁾. GamaSTAN should not be given to subjects with isolated immunoglobulin A (IgA) deficiency. Such persons have the potential for developing antibodies to IgA and could have anaphylactic reactions to subsequent administration of blood products that contain IgA. Other antibodies in the GamaSTAN preparation may interfere with the response to live virus vaccines such as measles, mumps, polio, or rubella, and varicella. Therefore, use of such vaccines should be deferred until approximately 5 to 6 months after GamaSTAN administration. When administering GamaSTAN as prophylaxis for measles, wait 5 months before giving measles vaccine to a non-immunocompromised subject and wait 6 months for an immunocompromised subject ⁽¹⁵⁾.

Local pain and tenderness at the injection site, urticaria, and angioedema may occur. Anaphylactic reactions, although rare, have been reported following the injection of human IG preparations. Anaphylaxis is more likely to occur if GamaSTAN is given intravenously; therefore, GamaSTAN must be administered only intramuscularly.

As with all preparations administered by the IM route, bleeding complications may be encountered in subjects with thrombocytopenia or other bleeding disorders.

Grifols' licensed Immune Globulin (Human) product, GamaSTAN S/D, is commonly administered as prophylaxis to provide active immunization following exposure to HAV, to provide pre-exposure prophylaxis for persons travelling to areas with endemic hepatitis A. GamaSTAN S/D is also indicated to prevent or modify measles, passive immunization against varicella, and prophylaxis in pregnant females exposed to rubella. The immediate administration of an IG product is intended to provide immediate passive virus neutralizing antibody coverage⁽²⁾.

Since the study treatment is not being given to subjects to treat any symptoms or illness, there will be no direct medical benefit from participation in this trial.

2.4 Description of and Justification for the Route of Administration, Dosage, Dosage Regimen, and Treatment Period(s)

2.4.1 Administration of Investigational Products

A single 0.2 mL/kg dose of the investigational product (IP) will be injected intramuscularly in the anterolateral aspects of the upper thigh or the deltoid muscle of the upper arm.

Doses over 5 mL are to be divided and injected into several muscle sites to reduce local pain and discomfort.

The gluteal region should not be used as an injection site due to the risk of injury to the sciatic nerve. The IP is not to be administered subcutaneously or intravenously.

2.4.2 Justification for Selection of Doses/Timing of Investigational Products

Recently the Food and Drug Administration (FDA) approved and instituted an anti-HAV titer specification (Not Less Than >20 IU/mL) and revised dosing for GamaSTAN S/D. Due to the recently instituted titer specifications and revised dosing, Grifols committed to the FDA to evaluate anti-HAV titers following IM administration at the recommended dose of 0.2 mL/kg in non-HAV (seronegative) healthy volunteers. An IM dose of 0.2 mL/kg was chosen, as it is the recommended dose for prophylaxis prior to exposure to hepatitis A for persons traveling to areas endemic with the virus.

Peak levels of IgG are obtained approximately 2 days after IM injection of immunoglobulins⁽¹²⁾. The half-life of IgG in the circulation of individuals with normal IgG levels is 23 days⁽⁹⁾. In this study, a 150-day follow-up period is chosen as it represents approximately 5 half-lives.

2.5 Compliance Statement

This study will be conducted under the conditions described in this protocol and in compliance with The International Council for Harmonisation of Technical Requirements for Pharmaceuticals for Human Use (ICH), Good Clinical Practice (GCP) and all applicable regulatory requirements.

2.6 Study Population

The study population will consist of HAV-seronegative healthy male and female subjects. Subjects must meet all the inclusion criteria and none of the exclusion criteria at the screening visit to be eligible for participation in this study. Continued eligibility will be assessed upon admission to the clinical site, prior to study treatment administration.

3 STUDY OBJECTIVES AND PURPOSE

3.1 Efficacy Objectives

The primary efficacy objective is to evaluate whether a single 0.2 mL/kg IM dose of the study treatment will provide protective levels of anti-HAV antibodies in HAV-seronegative healthy subjects for up to 60 days.

3.2 Pharmacokinetic Objectives

The pharmacokinetic (PK) objective is to evaluate the PK parameters of anti-HAV antibodies following a single 0.2 mL/kg IM dose of the study treatment in HAV-seronegative healthy subjects.

3.3 Safety Objectives

The safety objective is to evaluate the safety and tolerability of a single 0.2 mL/kg IM dose of the study treatment in HAV-seronegative healthy subjects.

4 STUDY DESIGN

4.1 Primary Endpoint and Secondary Endpoints

The primary efficacy endpoint is the proportion of subjects maintaining protective anti-HAV antibody levels (defined as anti-HAV antibody titer ≥ 10 mIU/mL in plasma and/or serum) up to 60 days after study treatment administration.

With respect to the PK endpoint, the parameters of interest for this study are: $AUC_{0-\infty}$, AUC_{0-T} , C_{max} , T_{max} , λ_z , T_{half} , Cl_{TOT}/F and V_D/F .

The safety endpoints will include a summary of the incidence of AEs, SAEs, suspected ADRs and ARs, as well as descriptive summary and statistics of the safety parameters (clinical laboratory values, vital signs and physical examination findings).

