Primary Efficacy Objective:

To evaluate whether a single 0.2 mL/kg intramuscular (IM) dose of the study treatment will provide protective levels of antibodies to HAV (anti-HAV) in HAV-seronegative healthy subjects for up to 60 days.

Pharmacokinetic (PK) Objectives:

To evaluate the PK parameters of anti-HAV antibodies following a single 0.2 mL/kg IM dose of the study treatment in HAV-seronegative healthy subjects.

The PK parameters of interest are:

- Area under the plasma and/or serum concentration time curve extrapolated to infinity ($AUC_{0-\infty}$)
- Cumulative area under the plasma and/or serum concentration time curve calculated from 0 to time of last observed quantifiable plasma and/or serum concentration (AUC_{0-T})
- Maximum observed plasma and/or serum concentration (C_{max})
- Time of maximum observed plasma and/or serum concentration (T_{max})
- Apparent elimination rate constant (λ_z)
- Terminal elimination half-life (T_{half})
- Apparent total plasma and/or serum clearance (Cl_{TOT}/F)
- Apparent volume of distribution (V_D/F)

Safety Objective:

To evaluate the safety and tolerability of a single 0.2 mL/kg IM dose of the study treatment in HAV-seronegative healthy subjects.

Overall Study Design and Description:

This is a single center, open-label, single-arm study. Approximately 28 HAV-seronegative healthy subjects will be enrolled in this study after obtaining their written informed consents. There will be a screening period of up to 28 days during which subjects will be screened for enrollment in the study.

The healthy subjects will receive a single IM dose of GamaSTAN (0.2 mL/kg), which is followed by a PK sampling period of 150 days (approximately 5 half-lives). The protective levels of anti-HAV antibodies will be assessed up to 60 days after the administration of GamaSTAN. A PK curve will be obtained during the PK sampling period.

Number of Subjects Planned:

Approximately 28 HAV-seronegative healthy subjects will be enrolled in the study which will provide about 20 evaluable subjects based on approximately 30% dropout rate.

Diagnosis and Main Criteria for Inclusion:

Only HAV-seronegative healthy adult subjects will be enrolled in this study.

Inclusion Criteria:

A subject must meet all the following inclusion criteria to be eligible for participation in this study.

1. Male subjects from 18 to 55 years of age, inclusive, or female subjects from 18 to 65 years of age, inclusive

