7 ASSESSMENT OF EFFICACY AND PHARMACOKINETICS

7.1 Efficacy Variables

7.1.1 Primary Efficacy Variable

The primary efficacy variable in this study is the proportion of subjects maintaining protective anti-HAV antibody levels (defined as anti-HAV antibody titer ≥ 10 mIU/mL in plasma and/or serum) up to 60 days after study treatment administration.

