7.3.3 Drug Concentration Measurements

Total anti-HAV antibody levels will be measured in the subjects throughout the study.

Table 7-2 PK Blood Sampling Schedule

Sample Number	Study Day	Time (Window)
01	1	Prior to treatment administration
02	1	60 minutes following treatment administration (±10 minutes)
03	1	12 hours following treatment administration (±1 hour)
04	2	24 hours following treatment administration (±1 hour)
05	3	48 hours following treatment administration (±4 hours)
06	4	72 hours following treatment administration (±4 hours)
07	5	96 hours following treatment administration (±4 hours)
08	7	(±1 day)
09	10	(±1 day)
10	14	(±1 day)
11	21	(±2 days)
12	28	(±2 days)
13	60	(±4 days)
14	79	(±4 days)
15	115	(±4 days)
16	150	(±7 days)

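### Does the primary endpoint need a stated starting sample for the period in which anti-HAV must stay at or above 10 mIU/mL?

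*Protocol*

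**What the plan says.** Protocol 4.1 and 7.1.1 define the primary variable as the "proportion of subjects maintaining protective anti-HAV antibody levels", with protective meaning a titer of at least 10 mIU/mL, "up to 60 days after study treatment administration". Section 9.1.2 ends the period at Day 60 instead. The synopsis (overall design) adds: "The protective levels of anti-HAV antibodies will be assessed up to 60 days after the administration of GamaSTAN". Section 3.1 states the objective as protective levels lasting up to 60 days.

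None of these places names the first sample that counts. Section 5.2 excludes anyone with anti-HAV antibodies at screening. Table 7-2 (7.3.3) schedules 13 samples through Day 60: one pre-dose, the next "60 minutes following treatment administration", then 12 hours, 24 hours and onward.

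On kinetics, 2.4.2 says: "Peak levels of IgG are obtained approximately 2 days after IM injection of immunoglobulins", and "The half-life of IgG in the circulation of individuals with normal IgG levels is 23 days".

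Section 9.1 leaves data handling and evaluation procedures to the SAP, and 9.6 leaves the detailed methodology there. Section 9.3 rules out hypothesis testing. Section 9.1.2 has all anti-HAV levels through Day 150 listed and summarized.

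**The concern.** A seronegative subject has no protective level to maintain at the moment of dosing. Administration is the only time anchor in the endpoint sentence, so a literal reader could count every post-dose sample, including the one at 60 minutes. Little of an intramuscular dose would have been absorbed by then if the peak comes at about 2 days. A subject well protected at Day 60 could be scored a failure on first-hour absorption alone, and the endpoint would then measure onset more than duration.

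The study is descriptive, open-label and single-arm, and this percentage is its primary result. Two defensible readings that gave very different percentages would matter, and a choice made after the levels were seen would be open to criticism.

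A smaller worry is that 60 days after dosing and Day 60 are not quite the same time.

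**Working it through.** **The plan's own figures.** The protocol states no expected 60-minute or Day 60 level, so there is none to reproduce. Its only design count is 28 enrolled for about 20 evaluable at about 30% dropout: 28 × 0.70 = 19.6, which agrees.

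**Inputs.** From 2.4.2: peak at 2 days and half-life 23 days, both stated for IgG and not for anti-HAV. From 4.4.1 and 4.4.1.1: 0.2 mL/kg and at least 20 IU/mL, so 0.2 × 20 × 1000 = 4,000 mIU/kg. Assumed, because the protocol plans only a non-compartmental analysis: one compartment, first-order absorption, zero baseline.

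**Model.**
- C(t) = (dose/V) × ka/(ka − ke) × [exp(−ke·t) − exp(−ka·t)].
- ke = ln 2/23 = 0.0301 per day.
- ka solves ln(ka/ke)/(ka − ke) = 2 days, giving ka = 2.168 per day.

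**Levels relative to dose/V.** Day 60 is 59 days after dosing under Table 7-2 numbering.

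| Time | C/(dose/V) | Ratio to Day 60 |
|---|---|---|
| 60 minutes | 0.0863 | 0.50 |
| 12 hours | 0.656 | 3.83 |
| 24 hours | 0.868 | 5.07 |
| Day 60 | 0.171 | 1 |

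In this model only the 60-minute post-dose sample lies below the Day 60 level. A subject passes at Day 60 with 10 mIU/mL, but passes every post-dose sample only with a Day 60 level of 10/0.504 = 19.8.

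**Sensitivity of the 0.50.**
- Half-life 23 days: 1.14 with the peak at 1 day (no conflict), 0.71 at 1.5 days, 0.30 at 3 days, and 0.12 with zero-order absorption ending at 2 days.
- Half-life 30 days, the value implied by the statement that "a 150-day follow-up period is chosen as it represents approximately 5 half-lives" (150/5), with a 2-day peak: 0.36.

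**Effect on the percentage.** Assume Day 60 levels are lognormal with CV 30%, so sigma = √ln(1.09) = 0.294, with the ratio fixed at 0.504 and no assay error.

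| Median Day 60 level (mIU/mL) | Pass at Day 60 | Pass every post-dose sample | Gap in 20 subjects |
|---|---|---|---|
| 12 | 73% | 4% | about 14 |
| 15 | 92% | 17% | about 15 |
| 20 | 99% | 51% | about 10 |
| 30 | 100% | 92% | about 2 |

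If the ratio itself varies between subjects with CV 40%, the third column becomes about 15%, 28%, 51% and 80%.

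**How plausible is the literal reading?** At minimum potency with an assumed V/F of 50 to 120 mL/kg, the 60-minute level is 4,000 × 0.0863/V = 6.9 to 2.9 mIU/mL at a 23-day half-life, and 7.4 to 3.1 at 30 days. That is below 10 throughout. The Day 60 level over the same range is 13.7 to 5.7, or 20.7 to 8.6 at 30 days. Counting the 60-minute sample would then leave almost no one passing, whatever happened later.

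**End of the period.** Table 7-2 equates Day 5 with "96 hours following treatment administration", so Day 60 is nominally 59 days after dosing. One day is worth 2^(1/23) = 1.03 in level. The permitted ±4 days is worth 2^(8/23) = 1.27 from edge to edge. One scheduled sample, Day 60 ± 4 days, serves both wordings.

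**The case for a change.** The strongest case for a change is that the SAP may settle how data are handled, but the protocol itself defines the primary variable in 4.1 and 7.1.1, and that definition is incomplete. The objective in 3.1 does not say whether onset counts. The gap between the readings could reach 15 of 20 subjects, and naming a first sample costs one sentence.

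Part of this stands. No section names a first qualifying sample, the arithmetic is right, and the 60-minute sample could matter if Day 60 levels fall between 10 and about 20 mIU/mL.

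The rest does not carry. Counted strictly from administration, the endpoint would take in the pre-dose sample, at which seronegative subjects are expected to be below 10. A reader who counts from 60 minutes has therefore already left the literal text and chosen a start. Once a choice is needed, maintaining presupposes a level that has been reached, and the objective is about how long protection lasts. The synopsis sentence says over what period levels are assessed, not which samples make a subject a success. Turning an endpoint sentence into a rule for each sample is commonly done in the SAP. The SAP is not available here, so its silence on this point cannot be assumed, nor can it be said that the rule would be set after levels are seen.

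The size of the gap also depends on a model, a variation and median levels that the protocol does not give.

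**Conclusion.** No change is called for. The endpoint leaves its first qualifying sample unstated, and analysts would fill that gap sensibly: the wording and the objective favor persistence from the time the level is reached, and the literal alternative is expected to fail every subject. The modeled 12-hour and 24-hour levels are 3.8 and 5.1 times the Day 60 level, so in the base case it makes no difference whether counting begins at 12 hours, at 24 hours or at the 2-day peak. Only the 60-minute sample separates the readings. Its ratio of 0.50 to Day 60 rests on an assumed absorption model and on IgG figures, and runs from 0.12 to 1.14 under other absorption assumptions at the same half-life.

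The consequence is also contained. There is no test or success threshold, and 9.1.2 lists every level, so the percentage under either reading can be recomputed from the listings. The two wordings of the end are a clerical variation: about 3% in level, inside the sampling window, with a single scheduled sample behind both.

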4.2 Study Design and Plan

[figure not shown]
This is a single center, open-label, single-arm study design, in which approximately 28 subjects will receive the same study treatment (0.2 mL/kg dose via IM injection). There is no reference therapy in this study.

The study will be explained to each subject prior to the subject providing written informed consent. All subjects will be screened to ensure that all the inclusion criteria and none of the exclusion criteria are met.

A sufficient number of subjects will be qualified by screening assessments and procedures for reporting to the clinical site on Day -1. Subjects will be discharged from the clinic on Day 2, following the scheduled assessments and procedures, and will return to the clinical site for the remaining ambulatory PK samples and safety monitoring, and again for the final visit (Day 150).

The total duration of study participation for subjects who complete the study will be approximately 178 days.

The Schedule of Study Procedures and Events is provided in [Appendix 1](#). The study consists of a Screening Visit, Treatment and Follow-up Visits, and Final Visit / Early Discontinuation Visit. The overall study schema is presented in [Figure 4-1](#).

^a PK sampling visits will be conducted as close as possible to the exact time points. The PK sampling visits: Day 1: prior to study drug injection, 60 minutes (± 10 minutes) post study drug injection and 12 hours post study drug injection (a window of ± 1 hour is permitted); Day 2 (window of ± 1 hour); Days 3, 4 and 5 (visits have a window of ± 4 hours); Days 7, 10, and 14 (all 3 visits have a window of ± 1 day); Days 21 and 28 (both visits have a window of ± 2 days); Days 60, 79 and 115 (all 3 visits have a window of ± 4 days); Day 150 (a window of ± 7 days)

Figure 4-1 Overall Study Diagram

4.3 Measures Taken to Minimize/Avoid Bias

4.3.1 Subject Numbering

Subjects in the study will receive a consecutive subject number. Subject numbers are generated beginning with the study center number (3 digits, assigned by the sponsor) followed consecutively with a unique number for each subject (4 digits, including leading zeros). For example, if the Investigator's center number is 301, subject number will be 3010001, 3010002, 3010003, etc., in consecutive order. Subject numbers, once assigned, will not be reused. If a subject is re-screened, a different subject number will be assigned to this subject.

4.3.2 Randomization

As this is an open-label, single-arm study design, no randomization code will be provided.

4.3.3 Blinding

Not applicable as this is an open-label study.

4.4 Study Treatments

4.4.1 Treatments to Be Administered

A single 0.2 mL/kg IM injection of GamaSTAN, administered in the anterolateral aspects of the upper thigh or the deltoid muscle of the upper arm.

Doses over 5 mL are to be divided and injected into several muscle sites to reduce local pain and discomfort.

The gluteal region should not be used as an injection site due to the risk of injury to the sciatic nerve. The IP is not to be administered subcutaneously or intravenously.

4.4.1.1 GamaSTAN

GamaSTAN (Immune Globulin ([Human]) is a 15 to 18% protein solution of human IgG for IM injection solution of human IgG for IM injection. GamaSTAN contains a minimum of 20 IU/mL of anti-HAV antibodies. GamaSTAN is a clear to opalescent, colorless to pale yellow sterile solution of polyvalent human IgG that contains no preservative.

GamaSTAN is provided in vials for single use. The batch number(s) of the study formulation will be indicated in the study files.

4.4.2 Labeling of Investigational Product

IP will be labeled according to the requirements of local law and legislation. Label text will be approved according to agreed Grifols procedures, and a copy of the labels will be made available to the study site.

4.4.3 Packaging of Investigational Product

The sponsor will be responsible for ensuring that the IP is manufactured in accordance with applicable Good Manufacturing Practice regulations and requirements.

4.4.4 Storage of Investigational Product

GamaSTAN must be stored in a secure location accessible only to study personnel authorized by the Investigator, such as the pharmacy staff responsible for the preparation and dispensing of IP.

GamaSTAN must be stored at 2 to 8°C (36 to 46°F). Do not freeze.

Investigators or designees are responsible for maintaining storage temperature records and for immediately reporting deviations in temperature to the study monitor. Continuous 24 hour, 7 days a week temperature monitoring is preferred. IP storage monitoring should be recorded and maintained by pharmacy staff. Copies of the storage temperature monitoring records will be made available for review by the Site Monitor, if applicable, during the course of the study and will be provided to the Sponsor at completion of the study. Details of receipt, storage, dispensing, and destruction will be recorded and maintained in the pharmacy log book by pharmacy staff.

Unused IP will either be destroyed according to local or institutional disposal regulations and regulatory requirement or shipped return to the Sponsor at the end of the study. The Sponsor will provide written instructions regarding final disposition of the unused IP. Copies of the IP storage and destruction records will be provided to the Sponsor at completion of the study.

